5.5 Use of radiation: N/A

5.6 Use of Center for Magnetic Resonance Research: N/A

6.0 Data and Specimen Banking

N/A

7.0 Sharing of Results with Participants

7.1 No individual results will be shared. If a participant requests the results of the study, a summary of the study results will be provided at study conclusion.

8.0 Study Population

8.1 Inclusion Criteria:

Study participants will be between the ages of 18 and 65, have diagnosed SMI, and be current daily smokers willing to attempt to quit or reduce their daily smoking. They must exhibit current stable psychiatric illness. Patients must be willing to either plan for a quit attempt or for cigarette reduction with a long-term goal of quitting.

8.2 Exclusion Criteria:

8.3 Our exclusion criteria include anyone who has had an active psychotic episode or been hospitalized within the past six months due to suicidal ideation or suicidal behavior. Anyone judged unable to give valid informed consent and unable to tolerate NRT will also

be excluded. Anyone who has had a heart attack in the past two weeks will be excluded. Additional exclusion criteria include regular use of tobacco products other than cigarettes, terminal illness (life expectancy of less than 12 months), or lack of a local address and telephone. If patients are currently taking the medications Clozapine/Clozaril or Chantix/Varenicline, they will be excluded from the study. Screening:

Hennepin County Medical Center Screening:

Patients at HCMC will be recruited into the study through two routes. The first is to receive a letter from HCMC that includes a brief description of the study and an HCMC phone number to call with questions. This letter will also give patients information on opting out of the chart review and subsequent screening phone call. The second is to get a referral to the study from the patient's medical/psychiatric provider. For those who do not opt out and for those who have a provider referral, an HCMC employee will reach out to patients over the phone to discuss the study and complete an eligibility screening. (SMI Smokers Screening Form V1.1) If a patient is eligible to proceed and interested in participating, the HCMC screener will forward the patient's information on to the UMN study staff who will reach out to schedule the in person baseline visit.

University of Minnesota Clinics Screening:

The outpatient Psychiatry Clinic in the Department of Psychiatry at the University of Minnesota provides new patients the opportunity to indicate whether they are interested in being contacted to hear about research studies or whether they prefer to not be contacted. Patients have the opportunity to sign the Psychiatry Research Registry Authorization form to participate in the Psychiatry Recruitment Registry when they come to the outpatient clinic for a visit. This authorization form gives the Clinical Research Advocate (CRA) access to their contact and health information to be added to the Psychiatry Research Recruitment Registry so that researchers recruiting for a study may contact them and inform them about possible opportunities they might be eligible for. Access to this contact information is managed by the Department of Psychiatry CRA. The CRA will provide us with a list of patients who have given their written consent to be contacted for research study opportunities and who meet our study's minimum requirements to be screened. The CRA will also hang posters and hand out study cards containing contact information to patients in the Department of Psychiatry. (Recruitment Card SMI Smoking and UMN SMI Smoking Recruitment Poster) UMN study staff will contact people on the list received from the CRA and complete an eligibility screening (SMI Smokers Screening Form V1.1). This same screening form will be used by UMN study staff if they are contacted directly by an interested patient.

9.0 Vulnerable Populations

9.1 Vulnerable Populations:

- Children
- Pregnant women/Fetuses/Neonates
- Prisoners
- Adults lacking capacity to consent and/or adults with diminished capacity to consent, including, but not limited to, those with acute medical conditions, psychiatric disorders, neurologic disorders, developmental disorders, and behavioral disorders
- Approached for participation in research during a stressful situation such as emergency room setting, childbirth (labor), etc.
- Disadvantaged in the distribution of social goods and services such as income, housing, or healthcare
- Serious health condition for which there are no satisfactory standard treatments
- Fear of negative consequences for not participating in the research (e.g. institutionalization, deportation, disclosure of stigmatizing behavior)
- Any other circumstance/dynamic that could increase vulnerability to coercion or exploitation that might influence consent to research or decision to continue in research
- Undervalued or disenfranchised social group
- Members of the military
- Non-English speakers
- Those unable to read (illiterate)
- Employees of the researcher
- Students of the researcher
- None of the above

9.2 Additional Safeguards:

The target population for this study is adults who have a diagnosis of a severe mental illness and who smoke. We will take all precautions necessary to ensure participants fully understand the purpose of the study, the requirements of participation, and what participation would entail. We will address any confusion about the study through a clear informed consent process that will include using the UCSD Brief Assessment of Capacity to Consent for Minimal Risk research. As mentioned in our background section, this is a population that is often overlooked for smoking cessation programs and that has voiced an interest in quitting smoking. Patients with

SMI tend to die at earlier ages than those without and it is important to reduce health risks, especially smoking.

10.0 Local Number of Participants

10.1 Local Number of Participants to be Consented:

We plan to recruit 60 participants for the study. However, we are requesting permission to enroll up to 80 participants to allow for early dropouts and inability to reach participants following initial enrollment in the study.

11.0 Local Recruitment Methods

11.1 Recruitment Process:

Patients will be recruited from those attending smoking cessation and/or psychiatric clinics at Hennepin County Medical Center (HCMC) and the University of Minnesota (UMN). We may also be displaying flyers at both HCMC and UMN clinics with a brief study description and contact information so that interested patients have the option to contact us as well. (Recruitment Card SMI Smoking, UMN SMI Smoking Recruitment Poster, HCMC SMI Smoking Recruitment Poster)

Hennepin County Medical Center Recruitment:

Patients at HCMC will be recruited into the study through two routes. The first is to receive a letter from HCMC that includes a brief description of the study and an HCMC phone number to call with questions. This letter will also give patients information on opting out of the chart review and subsequent screening phone call. The second is to get a referral to the study from the patient's medical/psychiatric provider. For those who do not opt out and for those who had a provider referral, an HCMC employee will reach out to patients over the phone to discuss the study and complete an eligibility screening. (SMI Smokers Screening Form V1.1) If a patient is eligible to proceed and interested in participating, the HCMC screener will forward the patient's contact information on to UMN study staff who will reach out to schedule the in person baseline visit.

University of Minnesota Clinics Recruitment:

The outpatient Psychiatry Clinic in the Department of Psychiatry at the University of Minnesota provides new patients the opportunity to indicate whether they are interested in being contacted to hear about research studies or whether they prefer to not be contacted. Access to this contact information is managed by the Department of Psychiatry Clinical Research Advocate (CRA). The CRA will provide us with a list of patients who are interested in being contacted for research studies and who meet our study's minimum requirements to be screened. The CRA will also hang posters and hand out study cards containing contact information to patients in the

Department of Psychiatry. If study staff are contacted directly by a patient in response to a poster, we will have a two-step process for verifying their mental health diagnosis. Step one will be to look for their name on the list received from the CRA. If they are not on the list, [name], an Assistant Professor and licensed clinical psychologist within the Department of Psychiatry who is Co-I on this study and has legitimate access to patients' medical records, will verify diagnosis.

After the screening process is complete:

Those who are interested and who meet initial eligibility criteria will be invited to the ECRC study site for further assessment and enrollment in the study. We plan to recruit a minimum of 60 participants with close to equal distribution from HCMC and UMN clinics. During the first in person visit, participants will be randomly allocated to the intervention or control group with approximately 30 in each.

11.2 Identification of Potential Participants:

We may be hanging flyers in the HCMC and UMN psychiatric clinics which contain study information. Patients who are interested in the study will then be able to reach out to study staff to get more information.

At HCMC, a chart review of patients attending smoking cessation or psychiatric clinics will be used to identify potential participants. Letters that include a brief description of the study, information about opting out of the recruitment phone call, and an HCMC study phone number will be sent to patients. HCMC medical and psychiatric providers may also refer their patients to the study.

UMN Department of Psychiatry maintains a database of patients who have agreed to be contacted about research studies. The Clinical Research Advocate will be using this database to find patients interested in being participants and will then run a query of the database to find patients who meet our minimum requirements to be screened.

11.3 Recruitment Materials:

In addition to the proactive methods described above, we may also place flyers describing the study and containing study contact information within the clinics so that patients may self-identify for the study. Study recruitment flyers are attached in the ETHOS recruitment section.

11.4 Payment:

Patients will receive a \$30 incentive for completing the baseline survey, a \$50 incentive for completing the 8-week survey, and a \$50 incentive for completing the final survey at six months post baseline assessment. All counseling sessions and related materials, including NRT, will be given to the patients free of charge. Participants will also be given \$30 to help cover the cost of transportation to the in-person sessions. If a candidate comes in

for the baseline visit and is deemed unable to give informed consent based on the results of the UCSD Brief Assessment of Capacity to Consent for Minimal Risk research, they will be given \$10 to help with travel expenses for the appointment.

12.0 Withdrawal of Participants

12.1 Withdrawal Circumstances:

Because we are using an intention-to-treat paradigm, subjects will be encouraged to continue their participation even if they are unsuccessful in quitting or making significant reductions in smoking. Participants may choose to withdraw from the study at any time without penalty. The PI and Co-PI may withdraw a patient from the study without their consent if that patient has an active psychotic episode or is hospitalized due to suicidal ideation or suicidal behavior. If this happens, trained study staff will have a conversation with the participant explaining the reasons for their withdrawal from the study.

12.2 Withdrawal Procedures:

If a participant withdraws from the study, no new data will be collected on that participant.

12.3 Termination Procedures:

If a participant is terminated from the study, no new data will be collected on that participant.

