4.2 Biosafety: N/A

4.3 Stem Cells: N/A

5.0 Procedures Involved

5.1 Study Design:

This is a randomized clinical trial that will enroll patients with documented SMI (ICD-10 codes) including schizophrenia, any other psychotic disorder, bipolar I and II disorder, and/or recurrent/chronic major depressive disorder into either a counseling intensive smoking cessation program or the control group.

5.2 Study Procedures:

This intervention is tailored to the needs of SMI smokers including addressing barriers to quitting and the need for continued supportive contact. Following is an outline of the study procedures:

Baseline assessment

Trained study staff will:

- Conduct informed consent
- Collect demographic and smoking history information along with current interest in quitting, readiness to quit, confidence in ability to quit, and nicotine dependence. We also will include mood, general psychiatric health, and quality of life questionnaires. (SMI Smokers BL Interview V1.1, SMI Smokers BL Self Report V1.1)
- Collect the name and phone number of an additional contact. Study staff will call the contact in the case of an emergency with the participant or if staff are unable to reach the participant for study visits. Staff will explain the two reasons for needing the additional contact person to the participant during the baseline visit.
- Randomize participants: prior to the baseline visit, we will complete a 1 to 1 non-stratified randomization. The randomization results will be put in envelopes to be opened during the baseline visit, determining if a participant will be allocated to the intervention or the control group.
- Conduct or schedule session one with those in the intervention group
- Distribute materials/resources to all participants.

Follow up assessments:

- Conducted at 8 weeks and 6 months post baseline assessment. (SMI Smokers 8 Week Interview V1.0, SMI Smokers 6 Month Interview V1.0,

and SMI Smokers 8W 6M Self Report V1.0, Study Satisfaction Survey V1.0 will be administered only at the 6 month assessment and only to participants in the Intervention group).

- Conducted in person when possible, but a phone option will be available.
- Measures will include current smoking status, quit attempts, self-reported number of cigarettes per day for those who currently are smoking, and interest and confidence in quitting/continued abstinence.
- Reported 7-day abstinence at 8 weeks and 6 months will be validated by an expired carbon monoxide sample.

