15.0 Statistical Considerations

15.1 Data Analysis Plan:

Feasibility analyses (e.g. recruitment rate, retention rate) and acceptability analyses (e.g., satisfaction scores, sessions attended, uptake of NRT) will be primarily descriptive. Given the limited number of participants, primary and secondary outcome analyses will be exploratory and will be used for effect size estimates for a potential larger future trial.

15.2 Power Analysis:

Although we are not powered to detect differences in abstinence, the current study will provide a necessary demonstration of the feasibility of our approach.

15.3 Statistical Analysis:

All analyses will be conducted on the intent to treat sample, with all randomized participants included in the analysis. We will estimate the effect of the intervention on smoking cessation (biochemically verified 7-day point prevalence abstinence) over 6 months using a single repeated measures regression model implemented with generalized estimating equations (GEE) and robust standard errors. Specifically, we will regress smoking status on intervention group and potential covariates using binomial errors, a logit link function, and a working unstructured correlation to accommodate within-subject correlation. For continuous secondary outcomes we will use linear regression models.

15.4 Data Integrity:

All study staffed will be trained on how to collect and store data. Data quality will be evaluated by study staff through review and assessment of gathered data to ensure completeness. Data will be kept in locked files or on a secure server, to both of which only authorized study personnel will have access. All identifying data will be stored separately.

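### Section 12.3 ends follow-up on participants the investigators remove after a psychiatric crisis, which creates avoidable missing outcomes in a plan that promises to analyze everyone randomized (minor)

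*Combined protocol and SAP*

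**What the plan says.** Section 12.1 opens by invoking an intention-to-treat paradigm as the reason for keeping people in the study when they fail to quit or cut down. It then gives the investigators a discretionary power: "The PI and Co-PI may withdraw a patient from the study without their consent". The triggers are an active psychotic episode and hospitalization for suicidal ideation or behavior.

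The consequence is in 12.3: "If a participant is terminated from the study, no new data will be collected on that participant". Section 12.2 has a parallel rule for people who leave by their own choice: "If a participant withdraws from the study, no new data will be collected on that participant".

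Section 15.3 sets the analysis population: "All analyses will be conducted on the intent to treat sample, with all randomized participants included in the analysis". The primary model is a GEE for biochemically verified 7-day abstinence, measured at 8 weeks and 6 months (3.1, 5.2). Section 15 has no rule for missing outcomes. Under 15.1 the outcome analyses are exploratory and "will be used for effect size estimates for a potential larger future trial".

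On follow-up visits, 5.2 says: "Conducted in person when possible, but a phone option will be available". Verification is by expired carbon monoxide (CO).

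**The concern.** A participant removed under 12.1 has not asked to leave. Removal ends the research contact as well as the treatment, so someone removed before week 8 has neither outcome and someone removed later has no 6-month outcome. The plan's own rule causes this loss, and for some of these people it is avoidable.

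The loss follows a clinical event after randomization, so it is doubtful that these outcomes are missing completely at random. That is the condition an unweighted GEE on available rows generally needs. Section 12.1 appeals to intention to treat for unsuccessful quitters, and 12.3 abandons it for people in crisis.

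At stake are the effect size estimates that 15.1 passes to a future trial and the retention figures that belong to the first study aim. A counting rule can be written later; an outcome never collected cannot be recovered.

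**Working it through.** **The sections side by side.** 12.1 sets the trigger and 12.3 stops collection. Neither discards data already obtained, so an 8-week result survives a later removal. 15.3 requires every randomized participant in the analysis. Both rules can be followed only by assigning a value to someone whose outcome the protocol declined to measure.

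**Inputs.** From the documents: about 30 per arm (11.1), two follow-up visits, no claimed power (15.2). There is no planned sample-size figure to reproduce. The documents give no removal rate, abstinence rate or planning parameters, so these are assumed: 6/30 versus 3/30 abstinent, removed participants smoking unless stated, and a larger trial at two-sided 5% and 80% power.

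**Formula.** Per arm, n = [1.960·√(2p̄(1−p̄)) + 0.8416·√(p₁(1−p₁) + p₂(1−p₂))]² / (p₁−p₂)², with p̄ the mean of p₁ and p₂.

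All randomized, 0.20 versus 0.10: [1.960·√0.255 + 0.8416·√0.25]² / 0.01 = (0.990 + 0.421)² / 0.01, which gives 199 per arm. The odds ratio is (6/24)/(3/27) = 2.25.

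**Observed-only, removal before the outcome is measured:**

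| Removed (intervention, control) | Proportions | Odds ratio | n per arm |
|---|---|---|---|
| 1, 0 | 6/29 vs 3/30 | (6/23)/(3/27) = 2.35 | 178 |
| 0, 1 | 6/30 vs 3/29 | (6/24)/(3/26) = 2.17 | 216 |
| 1, 1 | 6/29 vs 3/29 | (6/23)/(3/26) = 2.26 | 192 |
| 3, 0 | 6/27 vs 3/30 | (6/21)/(3/27) = 2.57 | 141 |
| 0, 3 | 6/30 vs 3/27 | (6/24)/(3/24) = 2.00 | 260 |

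The last two rows assume 10% removal in one arm and none in the other (3/30). They are an extreme case.

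**Why an analysis rule alone is not enough.** Suppose the single removed intervention participant was in fact abstinent. Full follow-up would give 7/30 versus 3/30, odds ratio (7/23)/(3/27) = 2.74 and 122 per arm. Counting that person as smoking gives 2.25 and dropping them gives 2.35. Neither recovers 2.74.

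**The planned GEE.** Assume 6 versus 3 abstinent at 8 weeks and 5 versus 2 at 6 months, with the 6-month abstainers among the 8-week ones. When everyone analyzed has both visits and group is the only term, the estimate equals the odds ratio over pooled visits.

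- All 60: (11/49)/(5/55) = 2.47, 95% CI 0.54 to 11.26, standard error of the log odds ratio 0.774.
- One intervention participant removed before week 8: (11/47)/(5/55) = 2.57, a shift of ln(2.574/2.469)/0.774 = +0.05 standard errors.
- One control removed before week 8: (11/49)/(5/53) = 2.38, a shift of −0.05.
- Three removed before week 8 from one arm only: 2.81 (intervention) or 2.20 (control), shifts of +0.17 and −0.15.
- Three intervention participants removed after week 8: 2.49, a shift of +0.01.

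**For scale.** One abstainer more or fewer in the intervention arm, with nobody missing, moves 199 per arm to 122 or 407.

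**The case against.** The case against giving this much weight is strong, and most of it stands.

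- **Removal is discretionary and probably rare.** Section 12.1 permits removal and does not require it. Section 8 asks for stable illness and excludes a recent psychotic episode or suicidality hospitalization. This stands.
- **An observed-only denominator is not what 15.3 plans.** A reader might take 141 to 260 per arm as the uncertainty the plan creates. It is not: an all-randomized analysis of verified abstinence most naturally counts the unverified as smoking, which gives 199 in every scenario above where removed participants smoke. The gap there is an unstated convention.
- **Cigarettes per day.** A reader might infer that a removed participant has no usable value, because 15.3 says "For continuous secondary outcomes we will use linear regression models". But 3.2 words the secondary outcomes as proportions achieving a result, including reduced cigarettes per day, and 15.3 does not name that outcome as continuous. Read as a proportion, a missing participant can be counted as not reduced.
- **Unequal removal.** A reader might infer that closer staff contact produces more removals in the intervention arm, and so a bias of known direction. The documents do not show this.
- **Section 12.2.** Stopping collection after a participant's own withdrawal is normal practice. It is not part of the fault.
- **Ending contact may protect a vulnerable person.** This is a fair reason to make follow-up conditional on clinical state and agreement. It does not justify a blanket stop for people who later recover and are willing.

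What remains is that 12.3 stops outcome collection on people who have not withdrawn consent, against the protocol's own stated principle.

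**Conclusion.** The point holds as a minor one. When used, the removal power in 12.1 combined with 12.3 causes avoidable missing 8-week or 6-month outcomes, at odds with intention to treat and with the analysis of all randomized participants.

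The size is modest. One removal in one arm moves an illustrative 199 per arm to 178 or 216 if someone analyzes observed cases only, and moves the planned GEE by about 0.05 standard errors either way. These figures rest on assumed abstinence counts and on removed participants smoking. The number removed is unknown and so is the direction of any bias. The documents do not support a claim that the trial's conclusions are threatened: outcome analyses are exploratory and no power is claimed.

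The absence of a counting rule is secondary. Section 15.3 already points toward one, but writing it down is worthwhile because 10.1 raises the enrollment ceiling to 80 "to allow for early dropouts and inability to reach participants following initial enrollment in the study". That covers recruitment and leaves the analysis of those exits unstated.

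**What to change.** 1. **Amend 12.1 and 12.3.** A psychotic episode or suicidality hospitalization may stop counseling and NRT, but not follow-up. In both arms, offer the existing 8-week and 6-month assessments when the participant is clinically able and agrees, in person with the CO sample where possible and otherwise by phone. Re-check capacity with the UCSD brief assessment already in the protocol. Stop collection only if consent is withdrawn or the participant is too unwell. Leave 12.2 unchanged.
2. **Clarify 15.3.** State that participants without verified abstinence count as smoking, with all randomized as the denominator, and give the observed-only result as a sensitivity analysis.
3. **Report exits by reason and arm.**

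Cost: a short amendment, one reason-for-exit field, and up to two extra assessments per affected participant on existing forms. Some will decline or be too unwell, so item 2 is still needed. A phone report can supply quit attempts and cigarettes per day but cannot verify abstinence, so it would count as smoking in the primary analysis. Counting missing as smoking is itself an assumption.
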